## **5.2 Analysis Sets**

Three main analysis sets will be used: the full analysis set (FAS), the per-protocol analysis set (PPAS) and the safety analysis set (SafAS).

### **5.2.1 Full Analysis Set**

The FAS will include all subjects who provided at least some data that will be used in the analysis of the secondary endpoints of the study. In this trial, the FAS will consist of all subjects who received at least one dose of vaccine and had at least one valid post-vaccination serology result.

### **5.2.2 Per-Protocol Analysis Set**

For each strain, subjects will be excluded from the PPAS for the following reasons:

- Subject did not meet all protocol-specified inclusion/exclusion criteria
- Subject received a vaccine other than the one that he/she was supposed to receive at Visit 1
- Preparation and/or administration of vaccine was not done as per protocol at Visit 1
- Subject did not provide a post-vaccination serology sample in the proper time window at Visit 2 for subjects aged 9 years or older or at Visit 3 for subjects aged 6 months to 8 years
- Subject received a protocol-restricted therapy
- Subject's serology sample at Visit 1 and after vaccination (on Visit 2 or Visit 3) did not produce a valid test result

For subjects from 6 months to 8 years old, the following deviations will also conduct to the exclusion of subjects:

- Subject received a vaccine other than the one that he/she was supposed to receive at Visit 2

**450 – Quadrivalent Influenza Vaccine**

---

- Preparation and/or administration of vaccine was not done as per protocol at Visit 2
- Subject did not receive vaccine in the proper time window at Visit 2

In the event of national immunization days for OPV, subjects who receive one or more doses of OPV at any time during the trial will not be withdrawn from the trial.

A subject will also be excluded if a deviation was assessed as having interfered with the vaccine response was reported. Such deviations will be identified through the data review process and be confirmed based on the clinical team decision.

**5.2.3 Safety Analysis Set**

The SafAS is defined as those subjects who have received at least one dose of the study vaccine.

**5.2.4 Populations Used in Analyses**

All subjects with data in the CRF will be taken into account in the description of the population. The immunogenicity analysis will be done on the FAS and confirmed on the PPAS. Finally, the SafAS will be used for the analysis of safety.

**5.3 Handling of Missing Data and Outliers****5.3.1 Immunogenicity**

Missing data will not be imputed. No test or search for outliers will be performed.

**5.3.2 Safety**

Missing safety data will not be replaced. No search for outliers will be performed.

**5.3.2.1 Immediate**

For unsolicited non-serious systemic AEs, a missing response to the “Immediate” field will be assumed to have occurred after the 30-minute surveillance period and will not be imputed.

For SAEs, missing or partially missing elapsed time from last vaccination recorded will remain missing and not be imputed. Such SAEs will not be considered as immediate.

**5.3.2.2 Causality**

Missing causality (relationship) for unsolicited non-serious AEs and SAEs will be considered at the time of analysis as related to vaccination.

**5.3.2.3 Measurements**

Partially missing temperatures will be handled as described in Section 4.3.1.1.1.

### 5.3.2.4 Intensity

For solicited reactions, missing intensities will be handled as described in Section 4.3.1.1.1. For unsolicited non-serious AEs, missing intensities will remain missing and will not be imputed.

### 5.3.2.5 Start Date and Stop Date

Missing or partially missing start dates for unsolicited AEs will remain missing and not be imputed. If either the start or stop date is missing or partially missing, the time to onset will be considered to be missing. Nevertheless unsolicited AEs with missing time to onset will be included in analyses according to the visit collected.

Missing or partially missing stop dates for AEs (solicited reactions and unsolicited AEs) will remain missing and not be imputed.

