**4.3.1.2.4 Time of Onset**

Time of onset is derived from the start date of the unsolicited non-serious AE provided in the clinical database and the date of last vaccination:

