**450 – Quadrivalent Influenza Vaccine**

---

- start date of the unsolicited non-serious AE – date of last vaccination

The time of onset should be considered as missing only if one or both of the dates are missing or partially missing.

The unsolicited non-serious AEs analyzed “Within 28 days” correspond to AEs with a time of onset between 0 and 28 days after vaccination or missing. An AE with missing time of onset will be considered having occurred just after the last vaccination, so will be included in these tables.

Note: Unsolicited non-serious AE that occur before vaccination (negative time of onset) or with a time of onset higher than 28 days will not be included in analysis but will be listed separately.

Time of onset will be displayed as follows:

- D0-D3
- D4-D7
- $\geq$  D8
- Missing

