**4.3.1.2.5 Duration**

Duration is derived from the start and stop dates of the unsolicited non-serious AE provided in the clinical database:

stop date of unsolicited non-serious AE - start date of unsolicited non-serious AE + 1.

The duration should be considered as missing only if one or both of the start and stop dates of the unsolicited non-serious AE is missing or partially missing.

Duration will be displayed by period as following:

1-3 days

4-7 days

$\geq$  8 days

Missing

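### SAP 5.3.2.5 sets time to onset to missing when only the stop date is incomplete, contradicting 4.3.1.2.4 and discarding a known onset for unsolicited non-serious AEs

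*SAP*

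**What the plan says.** Three parts of the SAP bear on this.

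- **Section 4.3.1.2.4 (Time of Onset, unsolicited non-serious AEs)** names the two dates that onset uses: "start date of the unsolicited non-serious AE provided in the clinical database and the date of last vaccination". Onset is the first minus the second. The section then limits when it may be missing: "The time of onset should be considered as missing only if one or both of the dates are missing or partially missing". It also requires a display ("Time of onset will be displayed as follows") with rows D0-D3, D4-D7, ≥D8 and Missing.
- **Section 4.3.1.2.5 (Duration)** uses the start and stop dates and has its own missing-data condition, which begins "The duration should be considered as missing only if one or both of the start and stop dates of the unsolicited non-serious AE" and ends by requiring that one of them be missing or partial.
- **Section 5.3.2.5 (Start Date and Stop Date)** says "If either the start or stop date is missing or partially missing, the time to onset will be considered to be missing". It leaves incomplete stop dates unimputed and adds: "Nevertheless unsolicited AEs with missing time to onset will be included in analyses according to the visit collected".

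On inclusion in the 28-day tables, 4.3.1.2.4 says of an event without an onset: "An AE with missing time of onset will be considered having occurred just after the last vaccination, so will be included in these tables". Of an event known to start late, it says that one "with a time of onset higher than 28 days will not be included in analysis but will be listed separately".

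**The concern.** The condition in 4.3.1.2.4 is exclusive: only the start date or the vaccination date can make onset missing. Section 5.3.2.5 adds a third cause, the stop date, which is not needed to compute onset. Both rules are operative text for the same derived variable, and the SAP does not say which prevails.

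Two programmers working from different sections would produce different onset tables from the same data. The one following 5.3.2.5 would discard an onset that had been recorded. The duration of such an event is already missing under 4.3.1.2.5, so its known onset would be lost as well. The trial tests no hypotheses (5.1.2.1), so the descriptive safety tables are themselves the result and their derivations should be unambiguous.

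**Working it through.** The plan gives no figure to reproduce. The check applies both rules to the same record.

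**Inputs**

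- Onset = AE start date − date of last vaccination (4.3.1.2.4).
- Rule A (4.3.1.2.4): onset is missing only if the start or vaccination date is incomplete.
- Rule B (5.3.2.5): onset is missing if the start or stop date is incomplete.
- Display rows D0-D3, D4-D7, ≥D8 and Missing, with a 28-day limit on analysed events (4.3.1.2.4).
- Next visit 28 days after vaccination, window ±2 days (Tables 3.1 and 3.2), so the latest in-window day is 28 + 2 = 30.

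**Where the rules differ**

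Take the vaccination date as known. If start and stop dates are both complete, the rules agree. If the start date is incomplete, both give Missing. They differ when the start date is complete and the stop date is not. Imputation does not remove the difference, because 5.3.2.5 leaves stop dates as they are.

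**Result for that record, by onset day**

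| Onset day | Number of days | Rule A | Rule B | In 28-day tables, A / B |
|---|---|---|---|---|
| D0-D3 | 3 − 0 + 1 = 4 | D0-D3 | Missing | yes / yes |
| D4-D7 | 7 − 4 + 1 = 4 | D4-D7 | Missing | yes / yes |
| D8-D28 | 28 − 8 + 1 = 21 | ≥D8 | Missing | yes / yes |
| D29-D30 | 30 − 29 + 1 = 2 | listed separately | Missing | no / yes |

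For example, an AE starting on day 2 with no stop date falls in D0-D3 under Rule A and in Missing under Rule B.

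On 4 + 4 + 21 = 29 onset days, only the category changes. On the last 2, which can occur only if the next visit falls after D28, inclusion may change too: Rule B makes the onset missing, and 4.3.1.2.4 then counts the event within 28 days. With the next visit on or before D28, no onset day changes inclusion. These are counts of calendar days, not of events.

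**Scope**

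- Solicited reactions are unaffected: their onset comes from daily intensities (4.3.1.1.4).
- SAEs use the same onset method (4.3.1.3.3), but 4.3.1.3.3 itself sets only two reporting periods, within 28 days and during the study. For a known onset after D28, only assignment to the 28-day period could change.
- A known onset before Visit 1 stays out under either rule (4.3).

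**The case against.** The strongest reply is that this is a drafting slip with little effect. Section 4.3.1.2.4 is the dedicated derivation section, with an explicit formula and an exclusive missing-data condition. A programmer would probably follow it, and the sentence in 5.3.2.5 reads like the duration condition carried over by mistake. That explanation is plausible but is an inference. The SAP states no order of precedence, so the conflict remains, although the loss of onset occurs only if 5.3.2.5 is followed.

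Second, the list in 5.1.2.2 describes unsolicited non-serious AEs by relationship and intensity and names time of onset only for solicited reactions; 4.2.2 says attributes are described according to the item. This limits the weight of the point. It does not remove it, because 4.3.1.2.4 itself requires the onset display, and the 5.1.2.2 entry ends on a comma and may be incomplete.

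Third, the D29-D30 case is not cleanly attributable to this conflict. Section 4.3 defines the analysed unsolicited AEs by visit interval, which would bring in a D29 event before a D30 visit whatever its stop date. For two-dose subjects, an event starting on the day of Visit 2 may also be assigned to the second dose by visit number (4.3.1.2.3). Out-of-window visits would alter the count of 2 days as well. These objections stand, and no weight is placed on that case or on the SAE extension.

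Finally, incidence, relatedness and grade do not depend on the onset category, and immunogenicity is untouched. That is correct.

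**Conclusion.** The contradiction is real, and 5.3.2.5 is wrong as written. It makes onset depend on a date that onset does not use. If followed, it moves an unsolicited non-serious AE with a known onset into the Missing row of the required display.

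Severity is minor. For onsets from D0 to D28 no event leaves or enters the 28-day tables; only the onset category is lost. A change of inclusion for a later onset is possible but probably rare, and it also depends on how 4.3 and 4.3.1.2.4 are read together.

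No percentage effect is claimed. The number of affected events depends on how many stop dates are incomplete and on how the stop date of an ongoing event is coded, neither of which the SAP gives. It does provide for incomplete stop dates in 4.3.1.2.5 and 5.3.2.5. If ongoing events are left with a blank stop date, they would be affected; if ongoing status is not treated as a missing stop date, few records may be.

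**What to change.** Replace the onset sentence in SAP 5.3.2.5 with text to this effect:

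> Time to onset is missing if the AE start date or the date of last vaccination is missing or partial. Duration is missing if the AE start date or the AE stop date is missing or partial.

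This brings 5.3.2.5 into line with 4.3.1.2.4 and 4.3.1.2.5. An AE starting on day 2 without a stop date would then appear in D0-D3, with only its duration missing. The rule that keeps events with missing onset in the analysis by visit can stay unchanged.

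The cost is one sentence of SAP wording. It needs no new data.

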### 5.3.2.6 Action Taken

Missing actions taken will remain missing and not be imputed.

## 5.4 Interim / Preliminary Analysis

Preliminary data line listings on subjects aged 18 years or older, 9 to 17 years, and 3 to 8 years will be prepared in the scope of the 3 early safety reviews.

No formal interim analyses are planned. However, the statistical analysis may be performed in 2 steps:

A first analysis of the immunogenicity and safety data from the 100 adult subjects will be performed once data are available and after first data base lock.

A final analysis at the end of the study when immunogenicity and safety data from all subjects are available and the final database lock.

## 5.5 Determination of Sample Size and Power Calculation

The sample size was set to 100 subjects per age group.

A 5% drop-out rate can be anticipated; therefore, 95 subjects per age group are expected to be evaluable for immunogenicity. With this sample size, the immunogenicity assessment in terms of percentages of subjects will have 95% CI widths of less than 21% (see Table 5.2).

**Table 5.2: 95% Confidence intervals for proportions (Exact method)**

n/N	% subjects observed	95% CI
45/95	47.40%	(37.0;57.9)
50/95	52.60%	(42.1;63.0)
55/95	57.90%	(47.3;68.0)

**450 – Quadrivalent Influenza Vaccine**

70/95	73.70%	(63.6;82.2)
90/95	94.70%	(88.1;98.3)
95/95	100.00%	(96.2;100.0)

For the safety assessment, a sample size of 100 subjects vaccinated will allow detecting with 0.95 probability an AE with a frequency of 3%.

**5.6 Data Review for Statistical Purposes**

A review of the data is anticipated through the data review process led by Data Management before database lock.

Three early safety data reviews for this trial are planned as described in Section 3.1.

- When the 100 adult subjects have been vaccinated and have provided safety data from D0 to D28 post-vaccination, using the data collection methods described in the protocol. The safety data collected will be entered into the electronic case report forms (CRFs), and will be reviewed by SEC experts. It is understood that this review is based on preliminary data that have not been subject to database lock. (The usual and ongoing process of monitoring safety signals outside of those specified in the protocol-defined early interim safety analysis will continue unchanged.)

The early safety review conducted by SEC experts will focus on the following adverse events (AEs) occurring within 28 days post-vaccination:

- Immediate reactions
- Solicited injection site and systemic reactions
- Unsolicited non-serious AEs
- SAEs
- When the 100 adolescent subjects aged 9 to 17 years have been vaccinated and have provided safety data from D0 to D28 post-vaccination, using the data collection methods described in the protocol. The safety data collected will be entered into the CRFs, will be reviewed by the Sponsor, and then submitted to the NDAC. It is understood that this review is based on preliminary data that have not been subject to database lock
- Similarly, when the 100 children subjects aged 3 to 8 years have been vaccinated and have provided safety data from D0 to D28 post-first vaccination. The safety data collected will be reviewed by the Sponsor, and then submitted to the NDAC.

